6.4 ECGs

All individual values for QT interval, QT interval corrected for heart rate by Bazett's formula (QTcB), and QT interval corrected for heart rate by Fridericia's formula (QTcF) will be presented in the data listings. QT, QTcB, and QTcF will also be included in the summary statistics.

All available non-missing values of ECG parameters should be used in the listings, summaries, and analyses for the double-blind and open-label treatment periods. However, if QTcF is missing and RR interval in seconds is available, then QTcF will be calculated as

$$QTcF = \frac{QT}{RR^{1/3}}$$

If both QTcF and RR in seconds are missing, then QTcF will be calculated as

$$QTcF = \frac{QT}{(60/HEART\ RATE)^{1/3}}$$

Although all recorded ECG parameter values, including abnormal ECG findings, will be included in the data listings, only quantitative values recorded at or near scheduled time points will be included in the summary statistics (see Table 10).

Table 10 Visit Windows for ECG

| Analysis visit | Target visit day | Analysis visit window |
|---|------------------|---|
| Baseline | 1 | Most recent non-missing pre-dose value |
| Week 24 | 169 | [1 (post-dose only), 266] |
| Week 52 | 365 | [267, the end day of the placebo-controlled period *] |
| * The end day of the placebo-controlled period is the last day before the first dose in OLE for subjects who enter OLE, and is the last day in study for subjects who do not enter OLE. | | |

6.4.1 Analysis of Central Tendency

Summary statistics (n, mean, SD, median, minimum, and maximum) will be presented for each ECG parameter and the corresponding changes from baseline by treatment and time point. Frequency distribution of maximum postdose ECG intervals tables will also be generated.

6.4.2 Categorical Analysis

The frequency distribution of subjects maximum recorded post-dose QTcF, PR, QRS, and Δ QTcF (change from baseline in QTcF) will be tabulated by treatment and summarized within the CSR for the following ranges:

- For QTcF: $QTcF \leq 450$ msec, $450 \text{ msec} < QTcF \leq 480$ msec, $480 \text{ msec} < QTcF \leq 500$ msec, $QTcF > 500$ msec
- For PR: $PR \leq 200$ msec, $PR > 200$ msec
- For QRS: $QRS \leq 120$ msec, $QRS > 120$ msec
- For Δ QTcF: $\Delta QTcF \leq 30$ msec, $30 \text{ msec} < \Delta QTcF \leq 60$ msec, $\Delta QTcF > 60$ msec

Individual QTcF, PR, QRS, or Δ QTcF values meeting these criteria will be flagged in the data listing.

6.5 Vital Signs

Vital sign parameters include body temperature, systolic blood pressure, diastolic blood pressure, heart rate, respiration rate and weight. The descriptive statistics for actual values and change from baseline will be summarized at each visit. Plot of mean vital sign values at each visit will be provided.

The analysis of vital signs will also focus on the incidence of clinically relevant outliers based on the following criteria. The incidence and percentage of clinically relevant outliers determined by each criterion will be summarized. A listing of subjects with clinically relevant vital signs will be provided.

Table 11 Criteria Used to Assess Potential Clinically Relevant Outliers in Vital Signs

| Variable | Low | High |
|--------------------------|--|--|
| Systolic Blood Pressure | <90 mm Hg or ≥ 20 mm Hg decrease from Baseline (BL) | >180 mm Hg or ≥ 20 mm Hg increase from BL |
| Diastolic Blood Pressure | < 50 mm Hg or ≥ 15 mm Hg decrease from BL | >105 mg Hg or ≥ 15 mm Hg increase from BL |
| Heart Rate | <50 bpm or ≥ 15 bpm decrease from BL | >120 bpm or ≥ 15 bpm increase from BL |
| Temperature | >2 degree C decrease from BL | >38.5 C or >2 degrees C increase from BL |

[REDACTED]

6.9 MRI Results

New post-baseline MRI findings will be summarized for (1) microhemorrhages, (2) macrohemorrhages, (3) superficial siderosis and (4) vasogenic edema.

A by-subject listing of MRI results is provided for enrolled subjects with new safety findings (i.e., those with a “Yes” response to the new safety findings question at any time during the study).

7 PHARMACOKINETIC DATA

CSF samples will be collected at protocol designated times for BIIB092 pharmacokinetic assessments from subjects [REDACTED]. Serum samples will be collected at protocol designated times for BIIB092 pharmacokinetic assessments from subjects.

7.1 CSF Concentration Data

The CSF PK analysis population will be used for the analysis of CSF concentration data.

CSF concentrations along with the scheduled (nominal) and actual sampling times (i.e., time from dosing) will be listed (when applicable) for each subject, group, and day. Differences between scheduled and actual sampling times will also be listed for all subjects. Percentage differences between actual administered dose and nominal dose will also be listed.

CSF concentrations below the lower limit of quantification (LLOQ) will be indicated by “BLQ”. For the purpose of calculating typical descriptive statistics (n, mean, SD, %CV, geometric mean, geometric %CV, median, minimum, and maximum) for CSF concentrations, all BLQ values will be set to half the LLOQ value. Mean CSF concentrations that are BLQ will be presented as BLQ, and the SD and %CV will be reported as not applicable. Summary statistics of the CSF concentrations will be tabulated by day and scheduled time point. At the discretion of the pharmacokineticist and/or biostatistician, samples may be excluded from descriptive statistics if there are large deviations between scheduled and actual sampling days or times, or large deviations between actual dose and nominal dose.

7.2 Serum Pharmacokinetics

The PK analysis population will be used for all listings, summaries, and statistical analyses. Analysis will include all valid data in the PK dataset for BIIB092. The listings will also include data from the OLE period.

Subject serum BIIB092 concentrations will be listed only.

Individual serum PK parameters C_{trough} and C_{inf} will be listed for BIIB092 including any exclusions. Summary statistics (including geometric means and coefficients of variation) will be tabulated for each PK parameter by visit. Plots of individual C_{trough} and C_{inf} over time will be provided.

Serum concentrations below the lower limit of quantification (LLOQ) will be indicated by “BLQ”. For the purpose of calculating typical descriptive statistics (n, mean, SD, %CV, geometric mean, geometric %CV, median, minimum, and maximum) for plasma concentrations, BLQ value pre day 1 of study treatment will be set to 0, all post first dose of study treatment BLQ values will be set to half the LLOQ value. Mean serum concentrations that are BLQ will be presented as BLQ, and the SD and %CV will be reported as not applicable. At the discretion of the pharmacokineticist and/or biostatistician, samples may be excluded from descriptive statistics if there are large deviations between scheduled and actual sampling times, or large deviations between actual dose and nominal dose.

Serum concentration vs. time (actual) profiles from Day 1 to Week 48, for each subject, as well as the mean (\pm SE) serum concentration vs. time (scheduled) profiles for the treatment group, will be presented graphically on linear and semilogarithmic scales. Samples may be excluded from the mean plots if there are large deviations between scheduled and actual sampling times, or large deviations between actual dose and nominal dose.

8 ANTI-DRUG ANTIBODY DATA

The anti-drug antibody (ADA) population will be used for the analysis of ADA data. All available ADA data will be listed. ADA data will be listed for subjects with any positive ADA result. Associations of ADA measures with PK and/or select AEs may be explored as needed.

The baseline value is defined as the last available value prior to first dose of placebo or BIIB092. For subjects with missing baseline assessment, the most conservative approach will be taken, and they will be considered negative for ADA at baseline.

The following definitions will be used in the analysis of ADA data:

- Treatment emergent positive:
 - A post-baseline subject sample that is positive when the baseline sample is negative; or
 - A post-baseline subject sample that has a titer greater than or equal to 4 times the baseline sample titer when the baseline sample is positive. If the titer value is not available for a positive baseline result, then the baseline titer value will be imputed as the minimum required dilution (MRD); or
 - A positive post-baseline result where no titer is available, regardless of baseline value
- Persistently positive: Two or more treatment emergent positive ADA results, where the time between the first and last positive results is 16 weeks or more; or if there are no further samples available 16 weeks or more following a treatment emergent positive result (including the OLE period).
- Transiently positive: more than one treatment-emergent positive evaluation, less than 16 weeks apart; or a single treatment emergent positive (not including pretreatment) when there are samples available 16 weeks or more following the positive result.

The following will be tabulated by treatment group: the number and percentage of subjects with any baseline sample that tested positive in the ADA assay; the number and percentage of subjects with any sample that tested positive in the ADA assay (including at baseline); the number and percentage of subjects with treatment emergent positive at each visit and at any time post-baseline; the number and percentage of subjects with persistently positive samples and similarly for transiently positive samples; the number and percentage of subjects with no treatment emergent positive ADA sample.

In this study, additional samples for ADA, referred to as “event driven” samples, may be collected for subjects with hypersensitivity events. ADA data will be listed for subjects with any event driven sample. Data from these samples will be considered part of a subject’s overall ADA assessment.

The analysis windows are defined based on the scheduled post-baseline visits for ADA in Table 13. The same visit windowing approach described in Section 6.1.2 will be used.

Table 13 Visit Windows for Anti-drug Antibody

| Analysis visit | Target visit day | Analysis visit window |
|-----------------------|-------------------------|--|
| Baseline | 1 | Last available value prior to the first dose of study drug |
| Week 4 | 29 | [1 (post-dose only), 42] |
| Week 8 | 57 | [43, 70] |

| | | |
|---------|-----|--|
| Week 12 | 85 | [71, 126] |
| Week 24 | 169 | [127, 210] |
| Week 36 | 253 | [211, 294] |
| Week 48 | 337 | [295, the end day of the placebo-controlled period*] |

[figure not shown]
* The end day of the placebo-controlled period is the last day before the first dose in OLE for subjects who enter OLE, and is the last day in study for subjects who do not enter OLE.

[figure not shown]

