8 ANTI-DRUG ANTIBODY DATA

Analyses for anti-drug antibodies (ADAs) will be based on subjects in the ADA population, defined as subjects in the safety population who had at least one post-dose evaluation for ADAs.

Active treatment period baseline will be used for ADA. If baseline is missing then it will be imputed as negative.

The following definitions will be used in the analysis of ADA data:

- Treatment emergent positive:
 - A post-baseline subject sample that is positive when the baseline sample is negative; or
 - A post-baseline subject sample that has a titer greater than or equal to 4 times the baseline sample titer when the baseline sample is positive. If the titer value is not available for a positive baseline result, then the baseline titer value will be imputed as the minimum required dilution (MRD); or
 - A positive post-baseline result where no titer is available, regardless of baseline value
- Persistently positive: Two or more treatment emergent positive ADA results, where the time between the first and last positive results is 16 weeks or more; or if there are no further samples available 16 weeks or more following a treatment emergent positive result (including the OLE period).
- Transiently positive: more than one treatment-emergent positive evaluation, less than 16 weeks apart, or a single treatment emergent positive (not including pretreatment) when there are samples available 16 weeks or more following the positive result.

The number and percentage of subjects with any sample that tested positive in the ADA assay (including at baseline), and the number and percentage of subjects without any positive post-treatment result (regardless of baseline) will be presented. The number of subjects with treatment emergent positive at each visit and at any time post-baseline will be presented; the number and percentage of subjects with persistently positive response and subjects with transiently positive responses will be presented similarly.

In this study, additional samples for ADA, referred to as “event driven” samples, may be collected for subjects with hypersensitivity events. Data from these samples will be considered part of a subject’s overall ADA assessment.

Associations of ADA with PK and/or select AEs may be explored.

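### The persistent and transient ADA definitions in both SAPs are not mutually exclusive: a participant with closely spaced positives and no later sample meets both

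*SAP*

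**What the plan says.** Section 8 of the placebo-controlled (PC) SAP gives each category two conditions joined by an alternative.

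- Persistent, condition A: "Two or more treatment emergent positive ADA results, where the time between the first and last positive results is 16 weeks or more".
- Persistent, condition B: "or if there are no further samples available 16 weeks or more following a treatment emergent positive result (including the OLE period").
- Transient, condition C: "more than one treatment-emergent positive evaluation, less than 16 weeks apart".
- Transient, condition D: "a single treatment emergent positive (not including pretreatment) when there are samples available 16 weeks or more following the positive result".

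Section 8 of the open-label extension (OLE) SAP repeats the four conditions; its transient rule begins "more than one treatment-emergent positive evaluation, less than 16 weeks apart, or a single treatment emergent positive". Neither SAP says that one category takes precedence or that the two exclude each other. In the PC SAP the counts are displayed by arm: "The following will be tabulated by treatment group". Protocol Section 14 and Tables 2 and 3 schedule post-baseline ADA samples at Weeks 4, 8, 12, 24, 36 and 48, then every 24 weeks in the extension from Week 76. No ADA sample is scheduled at Week 52, Week 64 or the Early Discontinuation visit.

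**The concern.** Condition B depends only on whether sampling continued. Condition C depends only on how close together the positives were. Nothing stops both being true of one participant: condition D asks for a later sample before calling a response transient, but condition C does not.

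A participant in that position is counted in both rows. The rows then do not partition the treatment-emergent positives, and the excess depends on who stops being sampled and when. Otherwise the programmer must invent a hierarchy that the plan does not contain. The overlap is not limited to early withdrawal, because the gap from Week 48 to Week 76 leaves late double-blind positives without a follow-on sample unless the participant is sampled in the extension.

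**Working it through.** The SAPs state no figure on this point, so there is nothing to reproduce. The check applies the four conditions literally to every positive/negative pattern on the nominal schedule.

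**Inputs.** Sample weeks 4, 8, 12, 24, 36, 48, then 76 and 100 (protocol Section 14, Tables 2 and 3). Threshold 16 weeks (SAP Section 8). Spacing of positives is taken as first to last.

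**Rules.** Let F and L be the weeks of the first and last treatment-emergent positive, and S the week of the last sample.

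- Persistent if (two or more positives and L − F ≥ 16) or S − L < 16.
- Transient if (two or more positives and L − F < 16) or (one positive and S − L ≥ 16).
- Both if there are two or more positives, L − F < 16 and S − L < 16.

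In condition B, any positive and the last positive give the same answer: if some positive has no sample 16 weeks later, the last one has none either.

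**Worked cases.**

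- Positive at 4 and 8, last sample 8: L − F = 4 and S − L = 0. Both.
- Positive at 36 and 48, last sample 48: L − F = 12 and S − L = 0. Both.
- Positive at 24 and 36, negative at 48, last sample 48: L − F = 12 and S − L = 12. Both.
- Positive at 36 and 48, negative at 76: S − L = 28. Transient only.

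**Full count.** With k post-baseline samples there are 2^k − 1 patterns with at least one positive.

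| Last sample | Patterns with ≥1 positive | Meeting both | Overlapping patterns (weeks positive) |
|---|---|---|---|
| Week 4 | 1 | 0 | none |
| Week 8 | 3 | 1 | 4+8 |
| Week 12 | 7 | 4 | 4+8, 4+12, 8+12, 4+8+12 |
| Week 24 | 15 | 4 | 4+12, 8+12, 4+8+12, 12+24 |
| Week 36 | 31 | 2 | 12+24, 24+36 |
| Week 48 | 63 | 2 | 24+36, 36+48 |
| Week 76 | 127 | 0 | none |
| Week 100 | 255 | 0 | none |

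No pattern met neither definition. If condition B is instead judged from the first positive, the overlap counts for last samples at Weeks 4 to 48 are 0, 1, 4, 1, 1 and 1, so the overlap does not depend on that reading. If closeness were judged on any pair of positives rather than first to last, it would be wider: positives at 4, 8 and 24 span 20 weeks (persistent by A) but include a pair 4 weeks apart (transient by C).

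**OLE SAP.** The same overlap applies to early-start participants with no extension ADA sample. For late-start participants the baseline is reset, and scheduled samples are 24 weeks apart (100 − 76 = 24). Two scheduled positives can therefore never satisfy condition C, and overlap there needs event-driven or post-withdrawal samples.

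**The case against.** The case on the other side has four parts.

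1. **Only a descriptive split is affected.** This stands. The secondary immunogenicity endpoint is the presence or absence of antibodies (protocol Section 4, PC SAP Section 2). The ADA-by-adverse-event tables use any treatment-emergent positive (PC SAP Section 6.2.3, OLE SAP Sections 6.2.4 and 6.2.5).

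2. **Some withdrawers are resampled.** Protocol Section 14 asks withdrawing participants with unstable or rising titers to return about every 6 weeks for up to 24 weeks. That can supply the missing later sample, but only for them.

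3. **Pattern counts are not a rate.** This also stands. The 114 participants not expected to complete (459 − 345) are a whole-trial figure, not a number affected.

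4. **The extension clause does not do what it might seem to.** In the PC SAP, "The baseline value is defined as the last available value prior to first dose of placebo or BIIB092", and that baseline is not reset at the switch. A reader might infer that antibodies arising after placebo participants switch to BIIB092 will be tabulated as persistent under placebo. The text does not establish this. The mention of the OLE sits on the condition about missing later samples. There, an extension sample removes default persistence: a lone Week 48 positive is persistent with no extension sample and transient with a negative Week 76 sample. Positives at Weeks 48 and 76 (28 weeks apart) become persistent only if extension positives count under condition A, which is not stated. PC SAP Section 3.1 limits that plan to the double-blind portion, and Table 13 closes its last ADA window the day before the first OLE dose; both point the other way. A further inference, that the arm difference in the secondary endpoint shrinks, also lacks support, since that endpoint does not use persistence.

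None of this removes the overlap itself.

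**Conclusion.** The point holds as a minor defect of definition in Section 8 of both SAPs. Followed exactly, the rules place anyone with two or more treatment-emergent positives less than 16 weeks apart, and no sample 16 or more weeks after the last, in both categories. Their counts can then exceed the total of treatment-emergent positives.

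The documents give no ADA rate, so the number of participants affected cannot be estimated. It is zero among those with a Week 76 sample on the nominal schedule. The enumeration assumes nominal visit weeks. Some gaps are exactly 16 weeks (Week 8 to Week 24), so the permitted visit windows could move individual cases either way.

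Whether extension positives count toward the PC classification is left open by the text. It is a matter to clarify, not a demonstrated bias against either arm.

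**What to change.** In Section 8 of both SAPs:

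- Define transient as a single treatment-emergent positive, or first and last treatment-emergent positives less than 16 weeks apart, and in either case at least one sample 16 weeks or more after the last positive.
- In the second persistent condition, refer to the last treatment-emergent positive rather than to any one.

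This is equivalent to calling a response transient only if it is not persistent. A span of 16 weeks or more is persistent; a shorter span, or a single positive, is transient if a later sample exists and persistent if not. The categories are then exclusive and exhaustive.

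In the PC SAP, also state whether positives from extension samples count toward this classification, and apply one data cut-off to both safety treatment groups. Cutting placebo alone at the first OLE dose would create an imbalance. A placebo participant whose only positive is at Week 36 or 48 would have no sample 16 weeks later (48 − 36 = 12) and be persistent by default. A BIIB092 participant with the same result and a negative Week 76 sample (76 − 36 = 40, 76 − 48 = 28) would be transient.

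The cost is a few sentences and a small programming change. The downside is that overlap cases leave the transient count and remain persistent, a slightly less favourable split.
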